5.5.2 Consent approach for minors (<16 years)

For children and young adults under 16 years of age, consent is required from a person with parental responsibility. Where this is not possible, consent may be sought from a personal legal representative. This may be a person not connected with the conduct of the evaluation who is suitable to act as the legal representative by virtue of their relationship with the child / young person, and is available and willing to do so. or a legal representative.

Those consenting on behalf of a minor, will be encouraged to discuss participation with the minor and reminded that their wishes should be respected. Weblinks to additional age-appropriate information sheets will be provided in the Participant Information Sheet for adults. These can be used to support discussions with minors to accommodate different competency levels.

5.5.3 Documenting digital or verbal consent

All in-person study procedures, including informed consent, will take place in line with site-specific infection control measures as it is imperative that all non-essential contact between the participants and evaluation team is prevented to minimise the risk of infection transmission. Stringent infection prevention and control procedures are deployed within each test setting to ensure transmission is minimised. As such, we will minimise contact by using a combination of digital consent and/or researcher recorded verbal consent in this framework.

Where informed consent is obtained remotely, the individual (or their consultee) will read and complete the Consent / Consultee Declaration Form provided and record their consent via the online UKHSA portal.

Where no digital confirmation of consent is provided by, or on behalf of, the participant, but where evaluation samples and data are returned to UKHSA, consent for their inclusion in the evaluation will be implied by the act of returning the samples and data.

Where a test site or organisation registers information on the individual's behalf (e.g. in a care home a professional staff member may complete the online registration on the residents behalf), the professional responsible for uploading the data, will be asked to confirm that consent was obtained for all participants prior to submission.

Where informed consent is obtained by a member of the study team or UKHSA testing operative, either in person or via the telephone, it will be done so verbally and documented via the online UKHSA results portal by the person taking consent.

5.6 Translation

It is important to note that we consider accessibility of testing to be a key part of the evaluations, and as such we would not look to exclude an individual from the opportunity to enrol in an evaluation because of language proficiency. The invite letter will direct participants requiring translated copies of information to the government/UKHSA website. This site contains guidance on the national testing programme and instructions for using the tests deployed by UKHSA provided in a number of alternative languages. Welsh translations will also be sent to individuals in Wales. Study information materials will be translated into other languages upon request.

6. STUDY PROCEDURES

This is a platform research protocol that is being set up to evaluate multiple point of care IVDD test kits, technologies and testing methodologies used for diagnosing and managing infectious diseases which are subject to UKHSA National Testing Programmes or other health protection responses.

This may involve participants performing testing or sample collection procedures themselves (self-test); performing self-testing procedures under the observation of a member of the study team, UKHSA testing operative, member of the health protection team or other healthcare professional (observed self-test); or test procedures administered or assisted by a trained professional (professional use)

Participants will receive standard of care testing alongside any evaluation test/method to ensure that participant care is not compromised. Participant's onward care pathway following a diagnostic test will be based on the standard of testing for that setting.

Participants will be provided with a study-specific Step-by-Step Participant Guide. Where they are performing in-person testing, the testing operative or healthcare provider will use this to guide the participant through the study procedures:

Participants (or their parent / care giver) will typically be asked to complete the following study-specific steps

1. Complete two (or more) IVDD tests in accordance with the IFUs provided. Participants will typically be asked to undertake:

- a. one comparator test – performed in accordance with standard care for that use-case/setting in accordance with UKHSA testing policy, and
 - b. one (or more) evaluation test(s) - performed either in accordance with standard care for that use-case/setting in accordance with UKHSA testing policy, or performed using an experimental IVD device, method or regimen which is different to standard care (e.g. a new device, a device used off-label, a different number or frequency of tests).
2. Additional samples may be collected from a subset of participants for in-vitro laboratory validation of IVDDs or for other service activities in line with a public health response (e.g. clinical characterisation of a virus). Samples collected for this purpose will not typically be considered to be diagnostic test and will be used only for research or quality assurance purposes subject to participant consent / consultee declaration. Such samples may be collected at the same time as the other tests or following confirmation of the diagnostic test result.
 3. Process any rapid point of care tests in accordance with their IFU.
 4. Enter the details of any diagnostic tests taken, rapid test results, current health status, demographic and other information (all of which are routinely collected) via the UKHSA web-based portal as described in a study-specific step-by-step guide.
 5. Return any PCR (or other laboratory processed) sample for analysis in accordance with study specific instructions as described in a study-specific step-by-step guide.

Participants (or their parent / caregiver) may be asked to provide additional information regarding their observations of the ease of use of the test where this is a new product planned to be or concurrently deployed across UKHSA. Ease of use observations may alternatively be collected from a healthcare professional, a member of the study team or a UKHSA testing operative in scenarios where they are observing or performing in-person testing.

The maximum number of tests/sample collections any participant may be asked to perform on the same day is expected to be three. However, it is anticipated that three tests will not be suitable for some use-cases and may deter participation. Therefore, this will only be considered where it is necessary to answer the research question and extra care will be given to the selection of the appropriate use-cases for inclusion in the study.

Evaluations may be conducted remotely with participants being sent the tests to complete in their homes, in a healthcare setting or in a social care organisation. Participant recruitment and/or other study procedures may also take place within UKHSA mobile testing units, test sites (including organisation led testing sites), participants homes or in other suitable public or commercial setting which are assessed as being suitable for such activities and approved by UKHSA.

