2. SYNOPSIS

Title	UKHSA Framework Protocol for Clinical Evaluation Studies of the Performance of In-vitro Diagnostic Devices (IVDD) in Detecting Covid-19 and Other Infectious Diseases	
Short Title	UKHSA IVDD Clinical Evaluation Framework Protocol	
Description and scope	This framework protocol provides the standardised approach to clinical studies evaluating IVDD technologies, methodologies and testing regimens selected by UKHSA for diagnosing and managing Covid-19, or other infectious diseases, as part of the national infectious disease testing programme.	
Sponsor	UK Health Security Agency	
Funder	UK Health Security Agency	
Aim / Objectives	Aims	Objective
	- To explore the performance of IVDDs to inform potential implementation or required adjustments within the	To gather new evidence on:

	
UKHSA's national infectious diseases testing programmes.
 
 - To generate generalisable new evidence to inform broader testing policy decisions. - To provide evidence of IVDD performance to the Medicines and Healthcare products Regulatory Agency (MHRA) in support of UKHSA's Emergency Use Authorisation and CE/UKCA marking applications. 	
 - The clinical performance of chosen testing technology, and/or sampling methodology. - The effectiveness of current or future planned testing regimens or approaches - The appropriateness and ease of use of testing service within chosen use-cases / settings.
Outcome Measures	Primary	Secondary
	Standard diagnostic accuracy of IVDD's relative to the relevant reference or comparator test (e.g. sensitivity, specificity, void rate).	Sensitivity stratified by covariates including viral load, symptom status, symptom duration, demography (gender, ethnicity, age, region). Usability data including surveys, questionnaires, observations or photographs/audio/video recordings
Intervention(s)	IVDD kits/ testing technologies / methodologies/regimen used for diagnosing and managing SARS-CoV-2, or other infectious diseases.	
Sample types	Sample types may include various swab types including: saliva, shallow nasal, breath condensate or sputum; skin or lesion swabs; scab collection or scrapings; finger prick samples; urine, faecal, vomit or semen samples; biopsy, blood or serum samples (where routinely collected).	

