6.3 IVDD Result Communication

There are two potential results pathways included in this framework. The first, most typical pathway is the diagnostic tests pathway. The other is the research sample pathway. Both approaches are described below:

- A. Diagnostic Tests: Tests which are intended to provide a clinical diagnosis to the participant. This may be their standard of care test, or another test completed in addition to standard of care, which may add some additional diagnostic value to the participant or their healthcare team.

Participants will be informed of the outcome of their laboratory processed diagnostic tests according to current UKHSA policy and procedures and will be provided with appropriate advice reflecting current UK public health guidelines. They will be advised to follow the appropriate guidance for the result of their diagnostic test(s).

All diagnostic Covid-19 test results are routinely reported to UKHSA testing service users via email and text. Positive results are also reported to their general practitioner via a digital update to the healthcare record delivered by NHS Digital. The exact mechanism of reporting results of other infectious diseases which may in future be subject to a UKHSA Testing Programme may vary in-line with clinical pathways. Appropriate public health guidance and links to further support will be provided in Step-by-Step participant guide. Where an evaluation involves completing multiple tests, the Step-by-Step Guide will include advice to account for a scenario where a person receives two conflicting results. This advice will reflect current public health guidance. This guidance is subject to change to reflect changes to national guidelines, the infectious disease in question and which tests are included in the evaluation. Where the

participant processes a test themselves (e.g. LFD tests or other rapid self-tests), regardless of whether this is for diagnostic or research purposes, the result will be available to the participant at the time of reading the test in accordance with the relevant IFU. Participants will be asked to report this result via the UKHSA online results reporting portal for it to be included in their care record and for the result to be included in the evaluation.

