13. DATA COLLECTION AND MANAGEMENT

13.1 Data Collection

Most study data will be obtained from the secondary use of routinely collected UKHSA testing information. Where additional information is required in relation to any user feedback or additional clinical or demographic information, required to address the specific study requirements, participants may be contacted by the study team and asked to provide the additional information via a short web-form or during a telephone call and will be kept to a minimum. Participants may also be asked to report ease of use by uploading a photograph of the completed test or a video of them performing the test.

If required, NHS Digital records may be accessed for any future sub-studies in order to perform a subset analysis for effectiveness of in-vitro Diagnostic Devices (IVDDs).

The four primary data sources include:

- Self-reported demographic and clinical symptom data provided by participants.
- Lab reported test outcomes.
- Self-reported test outcomes.
- Self-reported user feedback providing insights into the ease of use or acceptability of test or testing approach.

The following data may be captured or accessed, depending on the requirements of the specific study objectives.

Type	Item	Reason for collection
Contact details	Name	Routinely collected as part of UKHSA service user registration process. This data is required to communicate laboratory results to participants and permits follow-up by phone/text/email.
	Address	
	Telephone/mobile number	
	Email address	
Demographics	Gender	Routinely collected as part of UKHSA service user registration process. Required to monitor the representativeness of study sample to wider UK population.
	Age or age group	
	Ethnicity	
Clinical Details	Use Case / reason for testing	

	Symptom status (e.g., symptomatic / asymptomatic)	Routinely collected as part of UKHSA service user registration process. Testing performance is expected to be affected by these variables and therefore are typically included as secondary outcome measures in statistical analysis.
	Symptom type	
	Duration between symptom onset and taking the test	
	Person performing test (self/ healthcare professional / caregiver)	
Test Data	Test Type	Routinely collected as part of UKHSA laboratory analysis and reporting process.
	Test ID / barcode	
	Test Results (positive/negative/void/missing, variant type, CT values / viral load)	
	Test processing data (date/time processed/reported, laboratory)	

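### Symptom status and duration may be recorded after the rapid result is read, or at an unclear registration point, leaving symptom-stratified sensitivity open to misclassification

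*Protocol*

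**What the plan says.** The Synopsis lists as a secondary outcome "Sensitivity stratified by covariates including viral load, symptom status, symptom duration, demography" and further demographic factors. The Clinical Details block of the section 13.1 table explains why symptom items are collected: "Testing performance is expected to be affected by these variables and therefore are typically included as secondary outcome measures in statistical analysis".

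Two places bear on when these items are collected.

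- **Section 6, Study Procedures.** Participants "will typically be asked to complete the following study-specific steps". Step 3 is "Process any rapid point of care tests in accordance with their IFU". Step 4 is to "Enter the details of any diagnostic tests taken, rapid test results, current health status, demographic and other information", through the web portal and as set out in a study-specific guide.
- **Section 13.1, Clinical Details.** Symptom status, symptom type and "Duration between symptom onset and taking the test" are said to be collected routinely when the person registers as a service user.

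Section 6.3 adds that, where the participant processes the test, "the result will be available to the participant at the time of reading the test", whether the test is diagnostic or for research. Section 13.1 lists symptom data as self-reported. Section 8 states that participant-entered clinical data have no other source document against which they could be verified.

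**The concern.** A stratifying variable for test accuracy should be fixed without knowledge of the index result. If the steps are followed in the order written, a self-tester reports health status just after reading the rapid test. A positive result may prompt someone to report mild symptoms, and a negative one may lead someone to dismiss them. Index-positive cases then drift into the symptomatic stratum and index-negative cases into the asymptomatic one.

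The section 13.1 source raises a different problem. If registration precedes the test, symptom status can change in between, and the interval to the test is not yet known. Repeated testing, design (b) in section 5, makes a single early record less current still.

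At stake is the symptom-stratified secondary outcome. With no second source for the symptom data, misclassification could not be detected or corrected at analysis. Section 13.2 also foresees pooled analyses across studies, which would mix studies with different capture points.

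**Working it through.** The protocol gives no sensitivity, prevalence or sample size for this outcome, so there is no figure to reproduce. The check has a textual part and an illustrative calculation.

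**Text, side by side**

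1. Step 3 (test processed) precedes step 4 (health status and rapid result entered together). Section 6.3 confirms that a self-tester knows the result on reading it. Nothing in section 6 asks for symptoms to be entered before that.
2. Section 13.1 names registration. An interval ending at the test cannot be complete at a registration made before the test. Section 5.4 (Scenario 1) treats registering as a new user, ordering kits and returning a result as different occasions. Section 15.5 also speaks of registering the return of a sample. The term is therefore ambiguous.
3. Neither section requires recording at sampling and before the result is read.

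**Illustration (every rate below is an assumption)**

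Take comparator-positive participants in two truly equal strata, with true sensitivities Ss (symptomatic) and Sa (asymptomatic).

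*(a) Result-dependent reporting.* A share r of asymptomatic index-positives report symptoms, and a share s of symptomatic index-negatives report none.

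- Recorded symptomatic sensitivity = (Ss + r·Sa) / [Ss + r·Sa + (1 − s)(1 − Ss)]
- Recorded asymptomatic sensitivity = (1 − r)·Sa / [(1 − r)·Sa + (1 − Sa) + s(1 − Ss)]

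With 100 per stratum, Ss = Sa = 70% and r = s = 10%, 7 index-positives move to symptomatic and 3 index-negatives move to asymptomatic. This gives 77/104 = 74.0% and 63/96 = 65.6%.

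| True Ss / Sa | r = s | Recorded symptomatic | Recorded asymptomatic |
|---|---|---|---|
| 70% / 70% | 5% | 73.5/102 = 72.1% | 66.5/98 = 67.9% |
| 70% / 70% | 10% | 77/104 = 74.0% | 63/96 = 65.6% |
| 70% / 70% | 20% | 84/108 = 77.8% | 56/92 = 60.9% |
| 80% / 60% | 10% | 86/104 = 82.7% | 54/96 = 56.25% |

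In the last row a true gap of 20 points becomes 82.69 − 56.25 = 26.4 points.

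*(b) Outdated status.* A share m of those symptomatic at the test are still recorded as asymptomatic, whatever their result. Recorded symptomatic sensitivity stays at Ss. Recorded asymptomatic sensitivity = (Sa + m·Ss)/(1 + m). With 80% and 60%:

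- m = 10%: 68/110 = 61.8%, gap 18.2 points
- m = 30%: 84/130 = 64.6%, gap 15.4 points
- m = 50%: 100/150 = 66.7%, gap 13.3 points

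In every case overall sensitivity is 140/200 = 70%, because people only move between strata. The two mechanisms push the gap in opposite directions, and the primary result shows no sign of either.

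**The case against.** The strongest reply is that this is a framework. The steps are only typical, step 4 defers to a study-specific guide, and section 15.2 leaves each study's detail to its own SAP, procedures and guide. Nor is the numbered list a strict chronology: step 2 allows samples after a diagnostic result is confirmed, yet it precedes steps 3 to 5. Health status could be entered while a rapid test develops, and reading it as symptom status and onset is an inference. All of this stands, and it limits the point to a risk. It does not remove the point, because the only order the protocol sets out is the unfavourable one. Section 15.2 also says that guides within the framework's scope are not submitted for approval outside the sponsor.

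A reader might infer more than the documents support:

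- **That the strata do depend on the index result.** This needs a rapid index test read before entry. Laboratory-processed index tests are not open to it, because their results are not known at entry.
- **That sections 6 and 13.1 contradict each other outright.** The same table block includes who performed the test, which describes a test event. Section 5.5.3 uses online registration for care-home staff uploading data. Registration may therefore mean test-level registration, in which case the status need not be out of date.
- **That the symptomatic-asymptomatic gap is always exaggerated.** Outdated status would usually shrink it.
- **That deployment policy for asymptomatic testing rests on this contrast.** The protocol does not say so.

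It is also fair to object that earlier symptom capture cannot be imposed everywhere. Section 13.1 says most data are routine. Section 15.7.1 restricts care-home studies, where possible, to secondary use, and section 15.7.3 limits prisoners to observational studies within standard care. That stands and shapes the remedy.

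**Conclusion.** The point holds as a risk to a secondary outcome. For studies with a rapid index test read before data entry, the typical step order leaves sensitivity by symptom status and duration open to result-dependent classification. The wording of section 13.1 leaves it unclear whether earlier, possibly outdated, data would be used instead. A SAP cannot repair a covariate reported after the result was seen.

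The size is unknown. The calculation shows direction and plausible scale only, and rests on assumed sensitivities, equal strata and assumed shifts of 5% to 20%. Overall sensitivity and specificity are unaffected. This is a cheap improvement, not a flaw in the primary evaluation.

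**What to change.** Reconcile section 6 (steps 3 and 4) with the Clinical Details block of section 13.1.

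- **Consented studies with a rapid index test:** record symptom status and onset date at each sampling, before the rapid result is read, and enter only results afterwards. Derive duration from the onset and test dates. Under repeated testing, repeat the symptom entry for each test. State this capture point in the section 13.1 table.
- **Studies limited to routinely collected data:** state when symptoms were captured relative to the result, and report symptom-stratified sensitivity with that limitation.
- **In either case:** say what registration means in section 13.1.

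The questions themselves do not change. The cost is a reordered step, an amended table entry and one additional or split portal or kit-card entry per test episode in the consented studies. Where the routine service portal sets the timing, no change in capture is asked for, only disclosure.

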6.1 Sample Collection, Processing and Disposal

Biological samples to test for specific infectious diseases will be collected from all participants.

The types of samples collected will be determined by the type of IVDD under evaluation. Sample collection for a respiratory disease typically involves taking a swab sample from the nose and/or throat or collecting a small sample of saliva, breath condensate or sputum. However, other sample types which may be required include, finger prick, skin or lesion swabs, scab scrapings or scab collection, vomit, urine, faecal or semen samples. Blood or biopsy samples may also be required. However, these will be limited to diagnostic samples which are routinely collected as part of standard care and collected by trained healthcare professionals.

Samples may be collected using different sampling systems and materials, including transport mediums or methods of transport. All such approaches will be selected as appropriate for the specific requirements of the evaluation and shall be subject to clinical risk assessment by UKHSA, which will be undertaken during study planning.

All samples which require laboratory processing will be sent via courier or, where appropriate, priority post, to national laboratories and processed as part of the national testing programme.

All diagnostic samples will be processed and disposed of in accordance with IVDD manufacturer's instructions and standardised laboratory protocols. This includes, where appropriate, additional viral load analysis and genomic sequencing of positive samples to identify viral mutations.

Samples collected for laboratory-based quality assurance and technical validation of IVDD's will be retained with subject consent / consultee declaration and used only for the purposes for which they have consented. Any residual material which is stored be disposed of upon completion of the activity for which consent was obtained. Disposal will be in accordance with UKHSA laboratory standard operating procedures (SOPs).

